Participants will be recruited through convenience sampling of those working or training on the ICUs on days when it is possible to run the tasks. Individuals will not be recruited more than once.

Each participant will be given a numeric study ID and parameters recorded against this including:

- Job title- Consultant/fellow
- Gender- Male/female/prefer not to say
- Age- 21-30/31-40/41-50/51-60/61+
- Number of CVCs that they have previously inserted - <10, 10-50, >50).
- Time since last simulation training- 1 week/ 2-4 weeks/ 1-2 months / 3-6 months / 7-12 months / 1-2 years / >3 years

STUDY OUTCOMES

Primary Outcomes

Mean and standard deviation (accuracy) of time intervals measured.

Accuracy of retrospective recall of trends in monitored observations.

Secondary Outcomes

Impact of experience on time perception and monitoring changes.

STUDY PROCEDURES

Recruitment of participants

Participants will be provided with the information sheet appended and given the opportunity to ask any questions before consenting to the study. They will be asked to sign the appended consent form. Their consent forms will be in no way linked to the data collected such that participants could be identified from their data.

Randomisation

Block randomisation will be used to ensure even distribution of individuals at each grade of experience between the allocation groups. A block size of 4 will be used with 2 strata (grade= Consultant, Other). The randomisation list was determined by an online randomisation service ^[27]. The list generated is included as an appendix.

Two parts of the experimental process are randomised.

The first is the order in which the administrative and technical tasks are performed- this is randomised to remove the impact of primacy-recency impacts as well as task training through more practice with the timing apparatus.

The second is the scenario displayed on the monitor. As we are asking participants to identify a trend, randomisation to an increasing or decreasing trend reduces the likelihood of guessing the correct answer.

The study cannot be blinded at the time of data capture given the significant obvious differences between the tasks.

Study procedure

Structure

The overall structure is outlined below with further detail on each section provided in the following section.

Section order	Comment
Consent and discussion	To ensure valid consent and answer queries

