All equipment laid out on a table. The tissue pad is attached to the mannequin leg and surgically draped appropriately. The ultrasound probe is already in a sterile sheath, lying on the sterile field.

Instructions to subject

You are the fellow/consultant looking after Sophie. Sophie is a 2 year old girl with PIMS-TS. She is intubated and is stable on minimal ventilation and peripheral noradrenaline of 0.1mcg/kg/min. She has just been admitted to the unit. This is Sophie's bedspace, all the equipment you see is part of the simulation.

Your task is to request the admission investigations according to the sheet provided.

The nurse looking after the patient has had to step out of the bedspace to prepare their infusions and have asked you to complete your task whilst keeping an eye on the patient in the bedspace.

I am the nurse in the next bedspace, if at any point you want to make a clinical intervention please continue with the task and verbalise anything you would like me to do.

As before, when I ask you to begin, please press the foot pedal every 10 seconds, trying to be as accurate as possible. The task will last for several minutes.

Events during the task:

If this task is the first task undertaken, then the bedside monitor will display the same values throughout, aside from 1 desaturation. Heart rate: 125 bpm, blood pressure: 90/50 (65), respiratory rate: 25, oxygen saturations: 98%, end tidal CO₂: 4.5 mmHg. The oxygen saturation measure will fall to 88% for 5 seconds at 30 seconds into the task, triggering an alarm. This is to orient the participant to the monitor being part of the environment.

Normal values for age are: Heart rate: 80-140 bpm, respiration rate: 20-28 (APLS), 5th centile systolic: $65+(2 \times 2)=69$, 5th centile MAP: $50+(2 \times 2)=54$.

At 30 seconds into the task there will be a 10 second desaturation to 88% with spontaneous normalisation to 98%.

If this is the second task undertaken then values on the monitor will change during the task.

There are 2 monitor scenarios, 'A' and 'B'. Allocation between these is determined in the randomisation table (see appendix). They are identical apart from 'A' being a falling trend and 'B' a rising trend

- Scenario A
 - The oxygen saturation measure will fall to 88% for 5 seconds at 30 seconds into the task, triggering an alarm. This is to orient the participant to the monitor being part of the environment.

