 - The blood pressure will fall from an initial systolic/diastolic (mean) of 90/50 (63) at 30 seconds to 75/48 (55) at 4 minutes and then remain static at that level. There will be no alarm. This gradual drift tests participants' awareness and identification of monitoring trends during the task through what point they notice a change, if they do at all.

- Other parameters (heart rate, respiratory rate, oxygen saturations, end-tidal CO₂ and temperature) will not vary.
- Scenario B
 - The oxygen saturation measure will fall to 88% for 5 seconds at 30 seconds into the task, triggering an alarm. This is to orient the participant to the monitor being part of the environment.
 - The blood pressure will rise from an initial systolic/diastolic (mean) of 75/48 (55) at 30 seconds to 90/50 (63) at 4 minutes and then remain static at that level. There will be no alarm. This gradual drift tests participants' awareness and identification of monitoring trends during the task through what point they notice a change, if they do at all.
 - Other parameters (heart rate, respiratory rate, oxygen saturations, end-tidal CO₂ and temperature) will not vary.

End point:

6 minutes or completion of the task.

The participant will be asked for the time period they believe has elapsed between the first pedal press and the last.

3. Technical task

Inserting a CVC.

Equipment required:

- Child mannequin, intubated
- CVC insertion mannequin
- US machine + gel + probe cover
- CVC set
- Syringes, flush
- Cleaning- chlorprep lollipops
- Suture, needle holders, scissors, sharps bin
- Dressings + biopatch
- Gloves (non-sterile)
- Drape
- 5 +10ml syringes
- Sterile field drape
- Pen and paper for documentation
- Simulated bedside monitor
 - Varies observations over time in line with preset programming determined by the study team
- Foot pedal and data recorder for time logging

Setup

All equipment laid out on a table. The tissue pad is attached to the mannequin leg and surgically draped appropriately. The ultrasound probe is already in a sterile sheath, lying on the sterile field.

Instructions to subject

You are the fellow/consultant looking after Sophie. Sophie is a 2 year old girl with PIMS-TS who requires central access for inotropes. She is intubated and is stable on minimal ventilation and peripheral noradrenaline of 0.1mcg/kg/min. This is the Sophie's bedspace, all the equipment you see is part of the simulation

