 - Correct identification of no trends in other parameters - reported as proportion of participants correct
 - Accuracy of magnitude recall
 - The blood pressure either falls or rises between a systolic/diastolic (mean) of 70/48 (55) and 90/50 (65).
 - From the position of the x on the linear blood pressure scales we can derive:
 - The accuracy of the initial and final estimates compared with the actual values- reported for each task as the population mean and standard deviation of the percentage errors compared with the actual value.
 - The accuracy of the magnitude of the change, determined through comparing the difference in the estimated initial and final values compared with the actual 20mmHg systolic/ 10mmHg diastolic change for each task. The population mean and standard deviation of the percentage errors compared with the actual change will be reported for each task.
 - We hypothesised that there would be a priming effect following administration of the questionnaire, with participants more likely to attend to blood pressure trends if the questions were asked prior to the second task. We will therefore only ask the questions after the second task. We can then compare between the subgroups, split by which of the tasks was performed second to examine the impact of task type.
 - i.e the questionnaire analysis will have half the n of the overall study
- For the above we can compare subgroups using Fishers exact test.
 - By task order
 - By grade
 - By number of CVCs previously inserted

- By first 25% vs last 25% of participants

STATISTICAL CONSIDERATIONS AND DATA ANALYSIS

Sample size and statistical power

This is a pilot study and as such we do not expect it to be adequately powered to confirm hypotheses but intend that it should be hypothesis generating.

Statistical methods

The population summary statistics detailed above will be calculated using 'SPSS statistics' software with built-in min/max/mean/IQR/SD calculation.

With assumed normally distributed timing data and each participant completing 2 tasks the distributions will be compared with a paired sample t-test for; control vs administrative, control vs technical and administrative vs technical. For subgroup analysis paired or unpaired sample t-tests will be used as appropriate in each case. For the trend perception outcomes, contingency tables will be created for each subgroup and compared using Fishers exact test.

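### The summary of recalled initial and final pressures defines no absolute error and pools rising with falling scenarios, so its mean can measure bias instead of accuracy

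*Combined protocol and SAP*

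**What the plan says.** One of the two primary outcomes (Study outcomes) is "Accuracy of retrospective recall of trends in monitored observations". The Monitor trend perception analysis section builds on it in several ways: the proportion who noted a change, the proportion who identified the direction correctly, and numerical measures taken from marks on pressure scales.

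Two of the numerical measures matter here:

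- Initial and final values: the plan gives, by task, "the population mean and standard deviation of the percentage errors compared with the actual value".
- Size of the change: the difference between the two marks is "compared with the actual 20mmHg systolic/ 10mmHg diastolic change for each task". The summary takes the same form as for the initial and final values: "The population mean and standard deviation of the percentage errors compared with the actual change will be reported for each task".

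Neither sentence says whether the error is signed or absolute, and no absolute or squared error is defined elsewhere.

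The two monitor scenarios mirror each other: "They are identical apart from 'A' being a falling trend and 'B' a rising trend". Scenario A runs from "90/50 (63) at 30 seconds to 75/48 (55) at 4 minutes". For Scenario B, "The blood pressure will rise from an initial systolic/diastolic (mean) of 75/48 (55) at 30 seconds to 90/50 (63) at 4 minutes". The subgroups listed for the trend analysis are task order, grade, CVC experience, and first versus last quarter of participants. Monitor scenario is not among them, so A and B are pooled within each task.

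**The concern.** A percentage error is ordinarily the estimate minus the truth, divided by the truth, with its sign kept. Averaged over people, it measures bias. Here the truth for the initial reading is high in A and low in B, and the reverse holds for the final reading. Someone who did not follow the drift therefore tends to err in opposite directions in the two scenarios, and pooling lets those errors offset each other. A mean close to zero could then be read as accurate recall.

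A second consequence follows. Because errors in A and B have opposite signs, the pooled signed mean depends on the proportion of A and B in each task group. Two groups behaving identically can show different means.

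At stake is whether one component of a primary outcome can show what its label says it shows.

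**Working it through.** The plan gives no error figure or sample size for this measure, so there is nothing to reproduce. The check is direct arithmetic.

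**Inputs.** Systolic pressures come from Scenarios A and B: 90 to 75 in A, 75 to 90 in B. The A/B mix comes from the appended randomisation list. The participants' behaviours are assumptions.

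**Formula.** Error = 100 × (estimate − actual) / actual.

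**Case 1: everyone marks mid-range, 82.5, as the initial value.**
- A: (82.5 − 90)/90 = −8.3%
- B: (82.5 − 75)/75 = +10.0%
- Equal A and B: signed mean (−8.3 + 10.0)/2 = +0.8%; mean absolute error (8.3 + 10.0)/2 = 9.2%
- SD with 10 A and 10 B: 9.4 points

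**Case 2: the initial value is recalled correctly, the drift is missed, and the same value is marked as final.**
- A: (90 − 75)/75 = +20.0%
- B: (75 − 90)/90 = −16.7%
- Equal A and B: signed mean +1.7%; mean absolute error 18.3%
- SD with 10 A and 10 B: 18.8 points

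Case 2 is the more telling, because it is the plain failure to notice a trend and needs no unusual guess.

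**Mean pressure.** With 63 and 55, a mark of 59 as the initial value gives −6.3% (A) and +7.3% (B): signed mean +0.5%, mean absolute error 6.8%.

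**Where cancellation does not occur.** A fixed initial systolic mark of 75 gives −16.7% in A and 0% in B, a mean of −8.3%. A fixed mark of 90 gives 0% and +20.0%, a mean of +10.0%. In both, the signed mean equals the absolute error in size.

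**Effect of the A/B mix.** Over all 40 slots of the list, administrative first (so technical second) has 6 A and 4 B among consultants and 5 A and 5 B among others: 11 A and 9 B. Technical first (so administrative second) has 4 A and 6 B, plus 5 A and 5 B: 9 A and 11 B. With Case 2 behaviour in both groups:

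| Group | Signed mean | Mean absolute error |
|---|---|---|
| Technical second | (11 × 20.0 − 9 × 16.7)/20 = +3.5% | (11 × 20.0 + 9 × 16.7)/20 = 18.5% |
| Administrative second | (9 × 20.0 − 11 × 16.7)/20 = −0.2% | (9 × 20.0 + 11 × 16.7)/20 = 18.2% |

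The signed means differ by 3.7 points with no difference in behaviour; the absolute errors differ by 0.3.

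**Change measure.** An answer of no change scores −100% in both scenarios if the error is taken against the true change, so it does not cancel. An answer of the right size in the wrong direction scores 0% if only sizes are compared, and −200% if direction is kept. The plan does not say which applies.

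**Sensitivity to the reference values.** The analysis section gives systolic limits of 70 and 90 and means of 55 and 65, where the scenarios give 75 and 90, and 55 and 63. With 70 and 90, marking 80 throughout gives a signed mean of +1.6% and an absolute error of 12.7%; Case 2 gives +3.2% and 25.4%. The pattern is unchanged and the sizes are larger. The stated 10 mmHg diastolic change also does not match the diastolic values shown (50 − 48 = 2); it equals the change in the analysis section's mean pressures (65 − 55 = 10).

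**The case against.** The strongest reply has four parts.

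- **The sign is not written.** The text says only percentage errors, under the word accuracy, so absolute errors may have been intended. This stands as far as it goes: the defect is an undefined convention, with signed as the ordinary reading.
- **The SD is reported beside the mean.** This also stands. In the two systolic cases the SD is 9.4 and 18.8 points, which would alert a careful reader.
- **Cancellation depends on behaviour.** Marks at one end of the range do not cancel, and a participant who saw nothing may tick the box for not recalling the value and give no number.
- **Other measures address H_B.** The proportion noticing, the proportion with the correct direction, and the change measure all register unawareness.

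A reader might infer that unaware participants would look accurate overall, or that H_B could not be examined. The documents do not support that, because of those other measures and the SD. A reader might also want to express the problem as lost power. That is not supported either: the plan states no sample size, calls itself a pilot, and does not clearly specify a t-test of these errors.

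What the reply leaves untouched is that no absolute error is defined and the mirror-image scenarios are pooled. The SD does not repair the mean, which can still be near zero, or differ between groups, for reasons unrelated to accuracy.

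**Conclusion.** The concern holds for the initial and final pressure summary only. Read as signed, its mean measures bias and can be +0.8% or +1.7% when the typical participant is wrong by 9.2% or 18.3%. It can also separate two identically behaving groups by 3.7 points through their A/B mix. These figures rest on the signed reading, the Scenario A and B systolic values, the assumed response patterns, equal A and B numbers in the first two cases, and full use of the 40-slot list with every participant giving a value in the third. If absolute error was intended, there is no cancellation, but the plan still has to say so before the data are analysed.

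**What to change.** In the Monitor trend perception analysis section:

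1. Define absolute percentage error as the accuracy measure for the initial and final values, and compare it by which task was performed second. An estimated difference with a confidence interval suits a pilot.
2. Report the signed error separately for scenarios A and B, as a description of bias.
3. Define the change error relative to the true direction, so that a right-sized answer in the wrong direction is not scored as accurate.
4. Beside these, report by task group the proportion who ticked that they did not recall the value.
5. Before computing any error, reconcile the reference pressures between the scenario descriptions (systolic 75 and 90) and the analysis section (70 and 90), together with the mean pressures and the stated diastolic change.

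The cost is SAP wording and one derived variable from data already being collected.

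### The score for recalled size of the blood-pressure change uses one unsigned reference for a falling and a rising scenario, so backwards recall can score as correct

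*Combined protocol and SAP*

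**What the plan says.** All references are to the combined protocol and SAP.

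- Under Study outcomes, the second primary outcome is "Accuracy of retrospective recall of trends in monitored observations".
- Under Monitor trend perception analysis, one component is "The accuracy of the magnitude of the change", which is "determined through comparing the difference in the estimated initial and final values compared with the actual 20mmHg systolic" change, with a figure of 10 mmHg given for diastolic pressure. The summary is fixed as follows: "The population mean and standard deviation of the percentage errors compared with the actual change will be reported for each task".
- The same section gives the levels behind the reference: "The blood pressure either falls or rises between a systolic/diastolic (mean) of 70/48 (55) and 90/50 (65").
- Under the administrative task, Events during the task, the two monitor scenarios are described: "They are identical apart from 'A' being a falling trend and 'B' a rising trend". For scenario A, "The blood pressure will fall from an initial systolic/diastolic (mean) of 90/50 (63) at 30 seconds to 75/48 (55) at 4 minutes". Scenario B runs between the same two levels in the opposite direction. The technical task uses the same events.
- The questionnaire in the Appendix collects marks for initial and final systolic pressure and initial and final mean pressure. Each item has a box for participants who cannot recall the value.

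The text gives no sign convention, no order of subtraction, no separate reference by scenario, and no restriction to participants who recalled the right direction.

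**The concern.** The true change is negative in scenario A and positive in scenario B, but the score has a single positive reference and both scenarios are averaged within each task. If the marked difference is taken as an absolute size, the score cannot tell a participant who saw the pressure fall from one who believed it rose. It also credits guessers with a recalled change, because the absolute difference of two marks is never negative. If the difference is instead taken in one fixed order, the score is right in one scenario and badly wrong in the other.

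The score is summarised by task and belongs to a primary outcome bearing on H_B, that trend awareness is worse in the technical task. A loss of awareness in one task could therefore look smaller on this component than it is, or a task difference could arise from the scenario mix alone.

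**Working it through.** **Reference figure.** From the levels in the analysis section, 90 - 70 = 20 mmHg systolic, so the stated 20 reproduces there. It does not reproduce from the programmed scenarios, where 90 - 75 = 15 mmHg. The stated 10 mmHg diastolic matches the mean pressures in the analysis section (65 - 55 = 10), not the diastolic ones (50 - 48 = 2). The programmed mean change is 63 - 55 = 8 mmHg. Someone who recalls the programmed 15 mmHg exactly scores 100 × (15 - 20)/20 = -25% against the stated reference.

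**Scoring a participant who marks 90 and 70.** Percentage error = 100 × (D - 20)/20, with D defined in four ways:

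| Definition of D | A correct | A backwards | B correct | B backwards |
|---|---|---|---|---|
| Absolute difference | 0% | 0% | 0% | 0% |
| Final - initial, against +20 | -200% | 0% | 0% | -200% |
| Initial - final, against +20 | 0% | -200% | -200% | 0% |
| Signed by scenario | 0% | -200% | 0% | -200% |

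For example, correct recall of a fall under final - initial gives 100 × (-20 - 20)/20 = -200%. Three of the four definitions let a fully backwards participant score 0%. The pattern is the same with a 15 mmHg change and reference. Marking no change scores -100% under all four.

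**Guessers under the absolute difference.** Assumptions, none of them in the documents: displayed change and reference both 15 mmHg; aware participants average about 0% error; unaware participants make two independent normal marks with SD s about the same centre; 80% are aware in the administrative task and 50% in the technical task. The mean absolute difference of two such marks is 1.128s, so the mean error of unaware participants is 1.128s/15 - 1. The technical-minus-administrative contrast is (0.5 - 0.2) = 0.3 times that error.

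| s (mmHg) | Unaware mean error | Contrast, unsigned | Contrast, signed by scenario |
|---|---|---|---|
| 4 | -70% | -21 points | -30 points |
| 8 | -40% | -12 points | -30 points |
| 13.3 | 0% | 0 points | -30 points |

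Signed by scenario, unaware marks average -100% whatever their spread, hence 0.3 × -100 = -30.

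The result is sensitive to the marking model. With uniform marks over a scale of length L, the mean absolute difference is L/3. Against a 20 mmHg reference the unaware mean error is then -50% at L = 30, 0% at L = 60 and +150% at L = 150.

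**Scenario mix under a fixed order.** The printed randomisation list has 40 slots. Administrative-first (technical task second) has 11 A and 9 B; technical-first (administrative task second) has 9 A and 11 B. Suppose everyone recalls perfectly, the reference equals the displayed change, and D is final - initial. The means are then (11/20) × -200 = -110% with the technical task second and (9/20) × -200 = -90% with the administrative task second. That 20-point gap comes from scenario mix alone. In the consultant stratum (6 A/4 B against 4 A/6 B) the means are -120% and -80%, a 40-point gap. These figures assume every slot is filled. The opposite order of subtraction reverses the gap.

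**The case against.** Several points on the other side stand.

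- **Direction is scored elsewhere.** A rise/fall answer is taken straight after the second task, the questionnaire asks direction again, and the proportion with the correct trend is reported. A participant who reverses the trend is therefore marked wrong on that measure.
- **The levels are scored too.** In scenario A, marks of 75 then 90 give (75 - 90)/90 = -17% initially and (90 - 75)/75 = +20% finally, and an SD is reported.
- **The component is named as a size.** Scoring size and direction separately is a legitimate design. But nothing limits the size score to participants with the right direction, so it can still show good accuracy for people who recalled the opposite trend.
- **A signed mean can cancel as well.** One mark of 30 mmHg and one of zero average to a perfect 15. The fix therefore includes absolute error.

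A reader might infer that no reading of the rule works. The documents do not support that: the actual change could be taken as each participant's own signed change, and both problems then disappear. The text simply does not say so.

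A reader might also infer that unaware participants will average near zero error and hide a real loss of awareness. That needs absolute scoring and a particular mark spread. The marking scale is not shown, and the non-recall box may remove many guessers.

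**Conclusion.** The score is under-specified in a way that matters. On its plain reading, backwards and correct recall are indistinguishable, which follows from the arithmetic without further assumption. The dilution of a task contrast is conditional: from -30 points to about -21, -12 or 0 at mark SDs of 4, 8 and 13.3 mmHg, under the assumed 15 mmHg change, the 80%/50% awareness split and everyone supplying marks. Under a fixed order of subtraction the task mean depends on scenario mix, by 20 points if the whole printed list is used and recall is perfect.

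It would be too strong to infer that the primary outcome or the examination of H_B fails. This is one descriptive component, specified as a mean and SD. The proportions noticing a change and naming the correct trend are reported separately and compared with Fisher's exact test. The study is declared a hypothesis-generating pilot.

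**What to change.** In Monitor trend perception analysis, define the recalled change as marked final minus marked initial. Compare it with the signed change actually displayed in that participant's scenario (negative in A, positive in B), for systolic and for mean pressure. Percentage error = 100 × (recalled - displayed)/displayed, so correct recall scores 0%, no recalled change -100% and an exact reversal -200%.

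Report the mean and SD by second task, with the absolute error alongside because signed errors can cancel. Report by task the number who ticked that they could not recall the value. If a pure size measure is wanted, give it only among participants with the correct direction.

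Reconcile the reference change between the scenario descriptions (15 mmHg systolic, 8 mmHg mean) and the analysis section (20 mmHg systolic, with 10 mmHg labelled diastolic although the questionnaire collects mean pressure).

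The cost is a few sentences, since the marks and scenario allocation are already collected. The downside is that results will look less favourable where direction was recalled wrongly.
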